2 STUDY OBJECTIVES

This study will evaluate the efficacy, safety, and pharmacokinetics (PK) of LV in subjects with solid tumors. Specific objectives and corresponding endpoints for the study are summarized in Table 2-1.

Table 2-1: Objectives and corresponding endpoints

Primary Objective	Corresponding Primary Endpoint
Evaluate antitumor activity of LV	Investigator-determined confirmed ORR as measured by RECIST v1.1
Secondary Objectives	Corresponding Secondary Endpoints
Evaluate the safety and tolerability of LV	Type, incidence, severity, seriousness, and relatedness of AEs
Evaluate stability and control of disease	Investigator-determined DCR as measured by RECIST v1.1
Evaluate durability of response in subjects who respond to LV	Investigator-determined DOR as measured by RECIST v1.1
Evaluate PFS of subjects treated with LV	Investigator-determined PFS as measured by RECIST v1.1
Evaluate survival of subjects treated with LV	OS
Assess PK of LV	Selected PK parameters for LV, total antibody, and MMAE
Assess immunogenicity of LV	Incidence of ATA to LV
Additional Objectives	Corresponding Additional Endpoints
Assess biomarkers of biological activity and resistance and predictive biomarkers of response	Relationship between biomarkers in blood and tumor tissue to efficacy, safety, or other biomarker endpoints following treatment with LV

3 STUDY DESIGN

This global, open-label, multicenter trial is designed to assess the activity, safety, and tolerability of LV monotherapy for the treatment of solid tumors. Subjects with the following advanced solid tumors will be enrolled:

Cohort 1: SCLC

Cohort 2: NSCLC-squamous

Cohort 3: NSCLC-nonsquamous

Cohort 4: HNSCC

Cohort 5: esophageal squamous cell carcinoma (esophageal-squamous)

Cohort 6: gastric and gastroesophageal junction (GEJ) adenocarcinoma

Interim futility analyses will be performed separately for each cohort after at least 12 subjects of a given cohort have been treated and are efficacy evaluable post-baseline (Error! Reference source not found.). Enrollment to each cohort may be held after 12 subjects for interim futility analysis of the respective cohorts. The Bayesian predictive probability approach will be used to determine the futility criteria. At the time of each interim analysis, the predictive probability of success (PPoS) will be calculated. A PPoS <10% indicates that it is unlikely the objective response rate (ORR) will be better than the response rate of current standard of care at the end of the study given the interim result. Based on efficacy and safety data, together with the PPoS, a cohort may be stopped early by the sponsor.

In all subjects, LV will be administered by IV infusion at a dose of 2.5 mg/kg on Day 1 of each 21-day cycle. Dosing may not exceed 250 mg per infusion. An individual's dose may be modified based upon treatment-related adverse events (AEs). Tumor assessment according to Response Evaluation Criteria in Solid Tumors version 1.1 (RECIST v1.1) will be performed every 6 weeks for the first 12 months and then every 12 weeks thereafter. Objective responses will be confirmed with repeat scans 4-6 weeks after the first documentation of response.

4 ANALYSIS SETS

4.1 Full Analysis Set (FAS)

The full analysis set (FAS) includes all patients who received any amount of study drug. All efficacy analyses will be based on the FAS.

4.2 Safety Analysis Set

The safety analysis set includes all patients who received any amount of study drug, and thus is equivalent to the FAS. All safety analyses will be based on the safety analysis set.

4.3 Efficacy-Evaluable (EE) Analysis Set

The efficacy evaluable analysis set includes subjects who received any amount of study drug and had at least one post-baseline disease assessment per RECIST v1.1 or had clinical progression per investigator judgment or discontinued from study.

5 STATISTICAL CONSIDERATIONS

5.1 General Principles

In general, all analyses will be presented by cohort and total unless otherwise specified. Descriptive statistics will be presented that include the number of observations, mean, median, standard deviation, minimum and maximum for continuous variables, and the number and percentages per category for categorical variables.

Unless otherwise specified, confidence intervals (CI) will be calculated at 2-sided 90% level.

The 2-sided 90% exact CI using the Clopper-Pearson method will be calculated for the response rates where applicable (e.g., ORR) (Clopper 1934).

For time-to-event endpoints, the median survival time will be estimated using the Kaplan-Meier method; the associated 90% CI will be calculated based on the complementary log-log transformation (Collett 1994).

Any analysis not described in this plan will be considered exploratory, and will be documented in the clinical study report as a post hoc analysis or change to the planned analysis.

To comply with regulatory electronic submission guidelines, listings of all clinical data will be submitted as electronic data sets. To facilitate data review for the study report, only pertinent data listings will be created and attached to Section 16 of the CSR.

All statistical Tables, Listings and Figures will be produced using SAS[®], version 9.4 or higher. Other statistical software, if used, will be described in the CSR.

5.2 Determination of Sample Size

Up to 180 subjects may be enrolled in the study with up to 30 subjects enrolled in each cohort. In addition, the cohorts may be expanded to enroll additional subjects to better characterize LV activity. A cohort may be expanded to further characterize antitumor activity if the safety profile is acceptable, other efficacy endpoints are comparable to current standard of care, and the confirmed ORR meets cohort-specific criteria. Additional cohorts may also be added in future protocol amendments for additional indications, alternative dosing schedule, biopsy/biomarker analysis, and LV based combination therapy.

The sample size is not based on power calculations for formal hypothesis testing, but is selected to provide a degree of characterization of commonly occurring AEs in the safety profile.

For a sample size of 30 subjects per cohort, assuming confirmed ORR is between 10% and 50%, the 2-sided 90% exact confidence interval (CI) are summarized below:

Confirmed ORR	90% Exact CI (N=30)
10%	(3%, 24%)
20%	(9%, 36%)
30%	(17%, 47%)
40%	(25%, 57%)
50%	(34%, 66%)

This sample size of 30 patients per cohort would additionally provide the following probabilities of observing at least 1 patient having an AE, as summarized below.

True AE Incidence Rate	Probability of Observing at Least One Patient Having an AE (N=30)
5%	79%
10%	96%

5.3 Randomization and Blinding

This is a single arm, open label study. Randomization or blinding will not be performed.

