9.3.1.1. Randomization and Blinding

This is an open-label study. Blinding will not be performed. Cohorts in Part A and Part B are single-arm. The cohort in Part C has 3 randomized arms.

For Part C, approximately 90 subjects will be randomized to 1 of the 3 arms with 30 subjects per arm: Arm 1 (monotherapy 2q3wk), Arm 2 (2q3wk combination with pembrolizumab), Arm 3 (q1wk combination with pembrolizumab). The randomization ratio will be 2:1:1 until Arm 1 enrolls 30 subjects. This will ensure that Arm 1 reaches the target enrollment sooner. Thus, of the first 60 subjects, 30 subjects will be enrolled in Arm 1, 15 subjects will be enrolled in Arm 2 and 15 subjects will be enrolled in Arm 3. Afterwards, the remaining subjects will be randomized in a 1:1 ratio to either Arm 2 or Arm 3. Randomization will be stratified according to BRAF mutational status (wild-type versus mutated).

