9.3.5.1. Primary Efficacy Analyses

The primary endpoint of this study for all tumor types is the confirmed ORR per investigator assessment. The ORR is defined as the proportion of subjects who achieve a confirmed CR or PR according to RECIST v1.1. The ORR of each cohort and its exact 2-sided 90% CI using the Clopper-Pearson method ([Clopper 1934](#)) will be calculated.

For prostate cancer, confirmed PSA response per investigator assessment is another primary endpoint. The confirmed PSA response is defined as a reduction from baseline PSA level of at

least 50%, measured twice ≥ 3 weeks apart. The confirmed PSA response rate and its exact 2-sided 90% CI using the Clopper-Pearson method ([Clopper 1934](#)) will be calculated.

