1 INTRODUCTION

This document outlines the statistical methods to be implemented within the scope of Protocol SGNLVA-005, entitled “Open-Label Phase 2 Study of Ladiratuzumab Vedotin (LV) for Unresectable Locally Advanced or Metastatic Solid Tumors”, Original version dated 22Apr2019. Results of the proposed analyses will become the basis of the clinical study report for this protocol.

The purpose of this plan is to provide specific guidelines from which the analysis will proceed. All planned analyses specified in this document will be performed. Any changes to this plan, in the form of “post hoc” or “data driven” analyses will be identified as such in the final clinical study report (CSR). Any changes will either be reflected in amendments to this plan before the database lock or specifically documented in the CSR.

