6.5 Efficacy Analyses

All efficacy endpoints will be analyzed by cohort and total using the FAS. In addition, the objective response rate and disease control rate will be analyzed using the EE set.

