6.5.1 Primary Endpoint

6.5.1.1 Confirmed Objective Response Rate (ORR)

The primary endpoint of this study is the confirmed ORR per investigator assessment. The confirmed ORR is defined as the proportion of patients who achieve a confirmed CR or PR according to RECIST v1.1 (Eisenhauer 2009). Patients who do not have at least two post-baseline response assessments (initial response and confirmation scan) will be counted as non-responders. Confirmation means a PR is followed by a PR or CR at least 4 weeks later, or a CR is followed by a second CR at least 4 weeks later.

The confirmed ORR of each cohort and its exact 2-sided 90% CI will be calculated.

This endpoint will also be summarized by the subgroups defined in Section 0.

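### The SAP was not updated from the Original protocol to Amendment 04: as written it yields an efficacy total across different regimens and leaves the Part C arm-level ORR and the CRPC PSA analysis outside the SAP

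*SAP*

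**What the plan says.** SAP 1 ties the plan to the protocol's "Original version dated 22Apr2019". The rest of the SAP follows that design:

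- SAP 3 lists six tumour cohorts and one regimen: "In all subjects, LV will be administered by IV infusion at a dose of 2.5 mg/kg on Day 1 of each 21-day cycle".
- SAP 5.2 plans up to 180 subjects.
- SAP 5.3 states: "This is a single arm, open label study. Randomization or blinding will not be performed".
- SAP 4.1: "The full analysis set (FAS) includes all patients who received any amount of study drug".
- SAP 6.5: "All efficacy endpoints will be analyzed by cohort and total using the FAS".
- SAP 6.5.1.1: "The primary endpoint of this study is the confirmed ORR per investigator assessment". No PSA endpoint appears anywhere in the SAP.
- SAP 5.1 treats any analysis not described in the SAP as exploratory, to be reported as post hoc or as a change to plan.
- SAP 8.1 records no changes.

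The protocol is at Amendment 04 (02-Nov-2022). Section 9.3.1.1 says "The cohort in Part C has 3 randomized arms", with stratification by BRAF status. Section 9.3.5.1 gives the primary estimate as "The ORR of each cohort and its exact 2-sided 90% CI using the Clopper-Pearson method" and adds confirmed PSA response as another primary endpoint for prostate cancer.

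**The concern.** In the original design a cohort was one tumour type on one regimen, so reporting by cohort and in total was coherent. Under Amendment 04 a tumour type can span several regimens, and the all-dosed FAS spans all of them. Two things are at stake.

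The first is interpretation. An ORR averaged over q3wk, q1wk and 2q3wk dosing, and over LV with and without pembrolizumab, is not the response rate of any regimen under study.

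The second is prespecification. The SAP states that its analyses form the basis of the clinical study report and that anything outside it is exploratory. Part C reporting by arm and the CRPC PSA response would then lose prespecified status, although the protocol makes the PSA response a primary endpoint.

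**Working it through.** **1. Reproduce the SAP's own figures (SAP 5.2).** The exact two-sided 90% interval for x responders of n has lower limit equal to the 0.05 quantile of Beta(x, n−x+1) and upper limit equal to the 0.95 quantile of Beta(x+1, n−x). With n = 30:

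| x | ORR | Recomputed | SAP |
|---|---|---|---|
| 3 | 10% | 2.8, 23.9 | 3, 24 |
| 6 | 20% | 9.1, 35.7 | 9, 36 |
| 9 | 30% | 16.6, 46.5 | 17, 47 |
| 12 | 40% | 25.0, 56.6 | 25, 57 |
| 15 | 50% | 33.9, 66.1 | 34, 66 |

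The chance of seeing at least one AE is 1−0.95^30 = 78.5% and 1−0.90^30 = 95.8%, matching 79% and 96%. The SAP sample size is 6 × 30 = 180. The arithmetic is sound for the design it describes; the fault is scope and reporting unit.

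**2. Set the two documents side by side.**

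| Item | SAP | Protocol Amendment 04 |
|---|---|---|
| Allocation | single arm, none randomised | Part C: three arms, 2:1:1 then 1:1 (9.3.1.1) |
| Regimens | LV 2.5 mg/kg q3wk | q3wk; q1wk at 1.0 or 1.25 mg/kg; 2q3wk; 2q3wk and q1wk each with pembrolizumab (3.1) |
| Cohorts | 1–6 | 1–8 |
| Planned subjects | 180 | 72 + 252 + 90 = 414 (9.1) |
| Primary endpoint | confirmed ORR | confirmed ORR, plus confirmed PSA response in CRPC (9.3.5.1) |
| PSA response, PSA-DOR, PSA-PFS, PSA-evaluable set | absent | 9.2.2, 9.2.4, 9.2.7, 9.3.1.7 |
| Minimum interval for SD | 5 weeks | 5 weeks; 7 weeks for prostate (9.2.3) |
| PPoS columns | six | eight, with CRPC and melanoma (9.3.9) |

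**3. How much of the trial lies outside the SAP's regimen.** Only Part A matches it: 414 − 72 = 342, and 342/414 = 82.6%. At planned maxima the SAP 6.5 total would hold 72 subjects on q3wk LV, 252 on q1wk LV, 30 on 2q3wk LV and 60 on LV plus pembrolizumab (72 + 252 + 30 + 60 = 414; 60/414 = 14.5%).

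**4. Within Cohorts 1–6, if cohort is read as tumour type.** SAP 3 names cohorts by tumour only. A tumour type could have up to 12 subjects in Part A and 30 in Part B, so 42 together. The documents give no response rates for these cohorts; the counts below are assumptions. Exact 90% intervals, in per cent:

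| Part A | Part B | Combined |
|---|---|---|
| 0/12 = 0.0 (0, 22.1) | 6/30 = 20.0 (9.1, 35.7) | 6/42 = 14.3 (6.4, 26.3) |
| 1/12 = 8.3 (0.4, 33.9) | 6/30 = 20.0 (9.1, 35.7) | 7/42 = 16.7 (8.1, 29.0) |
| 1/12 = 8.3 (0.4, 33.9) | 9/30 = 30.0 (16.6, 46.5) | 10/42 = 23.8 (13.5, 37.0) |

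The combined figure falls 3.3 to 6.2 points below the Part B rate in these cases. In the last row its half-width is (37.0 − 13.5)/2 = 11.8 points, against (46.5 − 16.6)/2 = 15.0 for Part B alone. It looks more precise but describes neither schedule.

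**5. Does the protocol settle the unit?** In part. The synopsis (Statistical Methods) runs the primary analysis separately by cohort in Parts A, B and C. Section 9.1 gives precision at 30 per cohort or arm. Section 9.3.9 runs futility at a specific dose and schedule. But 9.3.5.1 asks only for the ORR of each cohort, and 9.3.1.1 calls the three Part C arms one cohort. Neither dose within Part B nor arm within Part C is named as the unit for the final ORR.

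**The case against.** The strongest defence has four parts.

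- **The SAP gives no express order to pool regimens.** SAP 6.5.1.1 asks for the ORR of each cohort; the total comes from the general statements in SAP 5.1 and 6.5. A total beside cohort rows does not replace them. This is right for the primary cohort estimates, but the total is still an ordered output, and on the current population it mixes regimens.
- **The protocol already separates the Parts and sizes precision by cohort or arm.** This stands, and it narrows the protocol gap to dose within Part B and arm within Part C.
- **The PSA analyses exist.** A reader might infer from the SAP that a CRPC primary endpoint has no planned analysis. The documents do not support that: the protocol gives its definition, analysis set, estimator and exact 90% interval. What is missing is the SAP text, and SAP 5.1 attaches a consequence to that.
- **Updating is foreseen.** Protocol 9.3 has the SAP finalised before database lock, SAP 1 allows amendment before lock, and SAP 5.2 anticipates new cohorts, schedules and combinations. This makes the problem easy to cure, but the current text remains wrong.

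A reader might also infer that the SAP directs one melanoma ORR over Part B and all three Part C arms. It does not: Cohort 8 is absent from the SAP. Those subjects would enter the all-subject total, but a single melanoma row would require extending the SAP to a cohort it never mentions.

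**Conclusion.** The point holds as a failure to update. Several rules stated in the SAP are false for the trial under Amendment 04: single arm, no randomisation, one regimen, six cohorts, 180 subjects and ORR as the sole primary endpoint. Followed literally, the SAP produces an efficacy total over different regimens and gives the Part C arm-level ORR and the CRPC PSA analysis exploratory or post hoc status. At planned maxima the mismatch covers 342 of 414 subjects.

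No type I error or power claim is affected, because the sample size is not based on a hypothesis test; the harm is to interpretation and prespecification. The mixing of Part A and Part B within Cohorts 1–6 depends on reading cohort as tumour type, and the sizes shown for it rest on assumed responder counts. The mismatch in design and endpoints, and the mixed total, depend on neither.

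**What to change.** Before database lock:

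1. In SAP 5.1, 6.5 and 7 and protocol 9.3.5, define the efficacy reporting unit as cohort within Part, dose/schedule and, for Part C, randomised arm. State to which regimen subjects are attributed if they cross from Part A to Part B or escalate within Part B, both of which protocol 3.1 permits.
2. Drop the all-subject efficacy total, or mark it descriptive only.
3. Replace SAP 5.3 with the content of protocol 9.3.1.1, including the BRAF stratum, and bring the protocol version, design, cohorts and sample size in SAP 1, 3 and 5.2 up to Amendment 04.
4. Carry into the SAP the protocol's confirmed PSA response as a primary endpoint for CRPC, PSA-DOR, PSA-PFS, the PSA-evaluable set, the 7-week SD minimum for prostate cancer, and the CRPC and melanoma PPoS columns.
5. Record these in SAP 8.

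The cost is one SAP amendment and a clarifying edit to protocol 9.3.5. By protocol 9.3, a change to analysis methods needs a protocol amendment only if it alters site conduct, which this does not. No new data and no further subjects are needed.

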5.4 Data Transformations and Derivations

5.4.1 General

Reported age in years will be used; if not available, age at informed consent in years will be calculated with the SAS® INTCK function (with method specified as “continuous”) using informed consent date and birth date.

Time variables based on two dates (e.g., Start Date and End Date) will be calculated as (End Date – Start Date +1 [in days]) unless otherwise specified in the planned analysis section.

Specifically, Study Day will be calculated as (Date–First Dose Date+1) for dates on or after the first dose date. The date of first dose will be Study Day 1. For dates prior to the first dose date, Study Day will be calculated as (Date–First Dose Date). For example, the date before the first dose date will be Study Day -1.

The following unit conversion will be implemented unless otherwise specified:

$$\text{Months} = \text{Days} / 30.4375$$

$$\text{Years} = \text{Days} / 365.25$$

Unless otherwise specified, baseline values used in all analyses will be the most recent non-missing measurement prior to the first dose of study drug.

The end-of-treatment (EOT) date will be the date the EOT visit is performed; if an EOT visit is not performed then the EOT date will be either the end-of-study (EOS) date or 30 days after the last dose of any study drug, whichever is earlier.

5.4.2 Best Response

The determination of antitumor activity will be based on objective response assessments made by the investigator according to the RECIST v1.1 (Eisenhauer 2009). Only response assessments on or prior to start date of any new anticancer therapy will be considered for best response. The patient's best response will be the best demonstrated response to date that has been confirmed, when confirmation is required (i.e. for PR and CR only). The patient's best response will be used in determining the ORR.

A response (CR or PR) will be considered confirmed if the subsequent disease assessment conducted no earlier than 4 weeks after the initial response still shows CR or PR. A patient will have a best response of SD if there is at least one SD assessment (or better) ≥ 5 weeks after the start of treatment and the patient does not qualify for confirmed CR or PR. RECIST v1.1 outlines scenarios for best overall responses when confirmation of CR and PR is required.

5.4.3 Response Assessment Dates

For efficacy assessments, the date of response assessment of CR, PR or SD will be the latest of all radiologic scan dates for the given response assessment. The date of progression per RECIST v1.1 will be the earliest of all radiologic scan dates for the given PD response assessment.

5.5 Handling of Dropouts and Missing Data

Missing data will not be imputed unless otherwise specified. Missing AE start date and/or end date will be imputed while calculating duration of events and treatment-emergent status (see Appendix A for imputation details).

For time-to-event endpoints, e.g., duration of response, time to response, PFS, and OS, patients who have no specific event will be censored as specified for each respective endpoint in Section 6.5.

Patients who do not have at least two (initial response and confirmation scan) post-baseline response assessments will be counted as non-responders for analysis of the primary endpoint.

Missing subsequent anticancer treatment start date will be imputed while deriving the time-to-event endpoints as applicable (see Appendix B for imputation details).

For prior therapies end dates, if month and year are present and only day is missing, day may be imputed. The imputed day will be the last day of the month if the prior therapy end date is earlier than the enrollment date based on the available month and year; the imputed day will be the day before enrollment if the prior therapy was stopped within the same month and year as enrollment. If month or year is missing, no imputation will be performed.

For prior therapies start dates, if month and year are present and only day is missing, day may be imputed. The imputed day will be the first day of the month. If month or year is missing, no imputation will be performed.

Unless otherwise specified, if the numeric value of a clinical laboratory test is not available because it is below the lower limit of quantification (LLOQ), “< LLOQ” should be used whenever applicable. In cases where a numeric value is required, e.g., calculating the mean and standard deviation, the LLOQ/2 will be used for the calculation.

5.6 Multicenter Studies

There are multiple centers in this study, however it is not anticipated that any center will accrue enough patients to warrant an analysis by center.

5.7 Multiple Comparison/Multiplicity

No multiple comparisons are planned in this study.

5.8 Examination of Subgroups

As exploratory analyses, subgroup analyses may be conducted for selected endpoints. Subgroups may include but are not limited to the following:

- Age (18–64, ≥ 65 years old)
- LIV-1 expression (high, low)
- Prior treatment with CPIs (yes, no)
- Prior treatment with taxanes (yes, no)
- ECOG performance score at baseline (0, 1)
- Number of prior systemic therapies (1, 2, 3, ≥ 4)
- Time since initial disease diagnosis (<6 month, ≥ 6 month)
- Time since initial metastatic/locally advanced disease diagnosis (<6 month, ≥ 6 month)
- Time since initial metastatic/locally advanced disease diagnosis (<3 month, ≥ 3 month)
- Time since end of the last prior systemic therapy (<3 month, ≥ 3 month)
- History of brain metastasis (yes, no)
- Liver metastasis at time of enrollment (yes, no)

If the number of patients in some subgroups is not sufficiently large (e.g., <5), the subgroup analysis may not be performed or the small subgroups may be combined if applicable.

